3.3 Early Withdrawal of Subjects

3.3.1 Criteria for removal from study

Insert subject withdrawal criteria (e.g., safety reasons, failure of subject to adhere to protocol requirements, subject consent withdrawal, disease progression, etc.).

Subject participation will be discontinued by recommendation of the team physician ([name]) if the subject experiences excessive pain during stimulation (>5/10), excessive tendon elongation (>3 cm), gapping at the repair site (>5 mm) or other AEs. Participants will also be removed if the outcomes from the repair surgery require patients to deviate from the standard rehabilitation protocol. An additional criteria include failure of the subject to adhere to the protocol and subject consent withdrawal.

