8.2 Sample size determination

If applicable, provide a justification of the sample size outlined in section 8.1 to include reflections on, or calculations of, the power of the study.

Two independent sample proportion comparison test was to compute the sample size using G* Power 3.1. A power analysis was performed based on the proportion of participants able to perform a heel rise at week 12, which is a strong predictor of long-term outcomes. With current rehabilitation strategies, 50% of participants are able to perform a single heel-rise at week 12. A clinically-significant improvement that would justify the application of the proposed treatment would be that 85% of participants would perform a heel-rise. A minimum of 22 subjects should be recruited in each group to achieve 80% power, with 5% significant level, equal allocation, to detect a significant difference between the two groups. Assuming an attrition rate similar to our previous studies of 10%, the total number of subjects in the NMES group should be 25.

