8.3 Statistical methods

Describe the statistical methods (or non-statistical methods of analysis) that will be employed.

We will recruit 25 participants to participate in the NMES intervention and 25 for standard rehabilitation (control). Summary statistics for variables of interest including recruitment, retention, adherence, and reported pain will be calculated. To test the difference between groups (NMES and control), we will quantify the odds ratio and the 95% confidence interval of performing a single heel-rise test. If the bottom end of the confidence interval is higher than 1.0, the improvement will be significant. Chi-square goodness of fit will be used to study the associations between groups and covariates such as gender, activity, and age. Cochran-Mantel-Haenszel test will be used to evaluate the consistency of such associations.

Protocol deviations, such as missing visits, or lost to follow up (within the 10% already considered in the power analysis) will have a negligible effect on the statistical analysis since the proposed analysis can have unbalanced groups. The planned interim safety analyses will quantify the odds ratio between adverse events in the intervention group and standard of care. If the bottom end of the confidence interval is higher than 1.0, the incidence of AEs in the intervention group will be significant higher than that of standard care.

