9.1 Periodic evaluation of data

Describe the plan to periodically evaluate the data collected regarding both harms and benefits to determine whether subjects remain safe.

The research team will monitor the recovery of the participant during standard-of-care visits and determine the occurrence of possible adverse related to Achilles tendon healing (re-rupture, deep vein thrombosis, deep and superficial infection) or the use of NMES (skin irritation and excessive pain).

Research team will capture and report all AEs at every visit. These AEs will be evaluated by a physician study team member ([name]) for their relatedness and severity. If the team member physician ([name]) prescribes a modification in the rehabilitation protocol or additional interventions (surgery), the patient will be removed from the study. Cumulative data will be evaluated every 2 months to determine if incidence of adverse events is higher than the normal (standard of care). The normal (standard of care) incidence of re-ruptures is 5% [4], [25], deep vein thrombosis is 48% [61], infection 2.8% [62], skin irritation 33% [63].

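### Participants can be removed before the only heel-rise test with no outcome follow-up described, and section 8.3 defines neither an analysis set nor a rule for a missing heel-rise

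*Combined protocol and SAP*

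**What the plan says.** The primary outcome is binary and is measured once, at week 12 (sections 1.2, 7.1 and 7.2).

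**Who can leave before then.**
- Section 3.3.1 discontinues participation, on the team physician's recommendation, "if the subject experiences excessive pain during stimulation (>5/10), excessive tendon elongation (>3 cm), gapping at the repair site (>5 mm) or other AEs".
- It adds: "Participants will also be removed if the outcomes from the repair surgery require patients to deviate from the standard rehabilitation protocol".
- It adds further: "An additional criteria include failure of the subject to adhere to the protocol and subject consent withdrawal".
- Section 9.1 says that if the physician "prescribes a modification in the rehabilitation protocol or additional interventions (surgery), the patient will be removed from the study".

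**What happens afterwards.** Section 3.3.2 allows use of data gathered before withdrawal. It provides for following adverse events until they resolve or stabilise, and for contact about new information or future studies. It does not mention a week-12 heel-rise.

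**What the analysis says.** Section 8.2 states: "Assuming an attrition rate similar to our previous studies of 10%, the total number of subjects in the NMES group should be 25". Section 8.3 opens its sentence on loss with "Protocol deviations, such as missing visits, or lost to follow up (within the 10% already considered in the power analysis" and concludes that these "will have a negligible effect on the statistical analysis since the proposed analysis can have unbalanced groups". It also plans some description: "Summary statistics for variables of interest including recruitment, retention, adherence, and reported pain will be calculated". Nothing in the document names the analysis set, says how a missing heel-rise is counted, or plans a sensitivity analysis.

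**The concern.** An odds ratio can be computed from arms of unequal size, so the 8.3 reason is true as far as it goes. It does not deal with who is missing. Section 1.1 says tendon lengthening is believed to contribute to functional deficits that include lower heel-rise height, and excessive elongation is one of the grounds for removal. People removed on such grounds may be less likely to manage the heel-rise. If so, an analysis of those tested favours whichever arm lost more of them.

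Only one ground, pain during stimulation, is exclusive to the NMES arm. The non-adherence ground covers the protocol in both arms, although NMES participants have more to adhere to. Elongation, gapping, other adverse events, altered rehabilitation and surgery can arise in either arm, and would be commoner in control if NMES helps healing. So the direction is open.

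At stake are the estimate itself and the fact that, with 25 per arm, how one or two untested people are counted can decide the result. The plan leaves that choice open until results can be seen.

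**Working it through.** **1. The plan's own figures.** Section 8.2 uses 50% vs 85%, 80% power and a 5% level. The pooled-variance formula, one-sided, gives

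n = [1.645·√(2·0.675·0.325) + 0.842·√(0.5·0.5 + 0.85·0.15)]² / 0.35² = 21.1, so 22 per group.

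The attrition step is 22/0.9 = 24.4, so 25. Both match. (A two-sided 5% level gives 27; that is a separate matter.) The 10% allowance therefore protects the number of completers. It says nothing about which participants are lost.

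**2. Bias with no true effect.**
- From the documents: 25 per arm (8.3); 50% success (8.2's control rate), set in both arms; benefit declared if the lower 95% limit of the odds ratio exceeds 1 (8.3).
- Assumed: the removal share r in each arm; the share f of those removed who would have failed; a Wald interval, with 0.5 added to each cell when a cell is zero.

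With true success p, the success rate among those still tested is q = [p − r(1 − f)] / (1 − r). The number tested is Binomial(25, 1 − r) and successes are binomial given that number. All tables were enumerated exactly. With no removal, the chance of declaring benefit is 2.2%.

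| Removed, NMES / control | f = 100% | f = 75% | f = 50% | Apparent OR at f = 100% |
|---|---|---|---|---|
| 8% / 4% | 3.5% | 2.9% | 2.5% | 1.10 |
| 12% / 4% | 4.9% | 3.5% | 2.4% | 1.21 |
| 8% / 12% | 1.6% | 2.0% | 2.4% | 0.90 |
| 4% / 12% | 1.1% | 1.7% | 2.4% | 0.83 |
| 10% / 10% | 2.4% | 2.4% | 2.4% | 1.00 |

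Example for 12% / 4% at f = 100%: the odds among those tested are 0.50/0.38 = 1.316 in NMES and 0.50/0.46 = 1.087 in control, a ratio of 1.21 although the true odds ratio is 1. At f = 50% removal is unrelated to outcome, because half would have failed anyway.

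**3. How often the counting rule matters.** Take the plan's 85% vs 50%, missingness unrelated to outcome, and two people untested. Analysing only those tested and counting the untested as failures reach different conclusions in 2.8% of trials (two untested in each arm) or 16.8% (two in NMES only). Worst-case and best-case counting differ in 45% and 24%; these are extreme bounds.

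**4. One deliberately borderline data set**, two untested in each arm (8% of 50):

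| Counting of the four untested | NMES | Control | OR (95% CI) |
|---|---|---|---|
| Left out | 19/23 | 12/23 | 4.35 (1.13 to 16.85) |
| All failures | 19/25 | 12/25 | 3.43 (1.03 to 11.48) |
| All successes | 21/25 | 14/25 | 4.13 (1.09 to 15.59) |
| Best case for NMES | 21/25 | 12/25 | 5.69 (1.51 to 21.42) |
| Worst case for NMES | 19/25 | 14/25 | 2.49 (0.74 to 8.35) |

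Only the worst case loses significance.

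**The case against.** The strongest reply is that the effect is small. In the table above, the 4.9% needs three times as much removal in NMES as in control and every removed participant failing. At 75% failing it is 3.5%, and with balanced removal it is 2.4%. The shares are assumed, any small binary trial shows wide worst-to-best bounds, and most countings of the example agree. All of that stands, and it limits the point to a correctable weakness. It does not supply the missing analysis set or rule.

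Readers might also infer more than the documents support:

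- *That the plan is biased towards NMES.* Only stimulation pain is exclusive to that arm, and several other grounds could remove more controls.
- *That 8.3 calls removals negligible.* Its sentence names missed visits and loss to follow-up within 10%. Removals are not addressed at all.
- *That every listed finding forces an exit.* Under 3.3.1, removal for pain, elongation, gapping or other adverse events rests on the physician's recommendation.
- *That 9.1 and 9.5 contradict each other on who leaves.* Section 9.5 lists removal, modified rehabilitation and further intervention as options that may be combined, which is compatible with 9.1.
- *That 3.3.2 forbids a later heel-rise.* It does not forbid one; it simply does not provide for it.

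The plan also deserves credit for its retention and adherence summaries, although these do not reach removals by arm and reason.

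**Conclusion.** The point holds as a gap that should be closed. The removal provisions, followed as written, can leave the primary outcome missing for reasons related to it; no passage secures that outcome; and the reason given in 8.3 answers a different question.

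Confidence is high in the omission. It is not high in any particular bias: the documents give no removal shares, so neither direction nor size is known. Under the stated assumptions the distortion near the planned 10% is modest in either direction, and it disappears when removal is balanced or unrelated to outcome. The percentages also rest on the Wald interval, which is an assumption of this check and not the plan's stated method.

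One neighbouring matter is separate and adds no weight here. Section 3.3.2 says both that recruitment continues until enough participants have complete data and that those who withdraw are not replaced, while 8.1 fixes enrolment at 50. These need to be reconciled.

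**What to change.** Leave every clinical criterion, and the decision whether a participant attempts the heel-rise, with the clinicians.

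1. **Sections 3.3 and 9.1:** state that stopping study treatment, or being removed, does not end outcome follow-up. Seek the already scheduled week-12 heel-rise from everyone who has not withdrawn consent.
2. **Section 8.3:** analyse all randomised participants by assigned arm. Fix one rule for a missing heel-rise, whatever the reason and the same in both arms, before outcome data are seen. Which rule is the sponsor's choice.
3. **Section 8.3:** add a sensitivity analysis that varies the missing outcomes separately by arm, including worst and best cases.
4. **Section 8.3:** delete the negligible-effect rationale and extend the retention summary to removals by arm and reason.

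**Cost.** The change is wording, plus week-12 contacts that are already scheduled. The estimate will reflect treatment as assigned.

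Counting every missing heel-rise as failure is one possible rule, and it has a price. At 25 per arm, 85% vs 50%, exact power is 77% with complete data.
- With 10% missing in both arms the rates become 0.85·0.9 = 76.5% and 0.50·0.9 = 45%, and power is 64%, against 71% if only those tested are analysed.
- With 10% missing in NMES only (76.5% vs 50%), power is 51%, against 73%.

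Nor is that rule neutral. With no true effect and missingness unrelated to outcome, the chance of declaring benefit is 0.9% if 10% are missing in NMES only and 5.0% if in control only. That is why steps 1 and 3 must accompany step 2.

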9.0 Data and Safety Monitoring Plan

This section is required when research involves more than Minimal Risk to subjects as defined in “HRP-001 SOP- Definitions.”

Minimal Risk is defined as the probability and magnitude of harm or discomfort anticipated in the research that are not greater in and of themselves than those ordinarily encountered in daily life or during the performance of routine physical or psychological examinations or tests. For research involving prisoners, Minimal Risk is the probability and magnitude of physical or psychological harm that is normally encountered in the daily lives, or in the routine medical, dental, or psychological examination of healthy persons.

Please complete the sections below if the research involves more than minimal risk to subjects, otherwise indicate each section as not applicable.

[Do not type here]

9.1 Periodic evaluation of data

Describe the plan to periodically evaluate the data collected regarding both harms and benefits to determine whether subjects remain safe.

The research team will monitor the recovery of the participant during standard-of-care visits and determine the occurrence of possible adverse related to Achilles tendon healing (re-rupture, deep vein thrombosis, deep and superficial infection) or the use of NMES (skin irritation and excessive pain).

Research team will capture and report all AEs at every visit. These AEs will be evaluated by a physician study team member ([name]) for their relatedness and severity. If the team member physician ([name]) prescribes a modification in the rehabilitation protocol or additional interventions (surgery), the patient will be removed from the study. Cumulative data will be evaluated every 2 months to determine if incidence of adverse events is higher than the normal (standard of care). The normal (standard of care) incidence of re-ruptures is 5% [4], [25], deep vein thrombosis is 48% [61], infection 2.8% [62], skin irritation 33% [63].

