7.2 Study Procedures

Provide a step by step description of all research procedures being conducted (broken down by visit, if applicable) including such information as below (where and when applicable); describe the following:

- HOW: (e.g., data collection via interviews, focus groups, forms such as surveys and questionnaires, medical/school records, audio/video/digital recordings, photographs, EKG procedures, MRI, mobile devices such as electronic tablets/cell phones, observations, collection of specimens, experimental drug/device testing, manipulation of behavior/use of deception, computer games, etc.)
- WHERE: (e.g., classrooms, labs, internet/online, places of business, medical settings, public spaces, etc.)

All participants participating will receive a standard rehabilitation protocol. All participants will be randomly assigned to NMES or control (standard of care) for the first 6 weeks after surgery. For the randomization process, a master list with patient codes will prepopulated with randomly assigned treatments (NMES vs control). As recruitment is performed, patients will be assigned a code with the corresponding intervention. The randomization will be performed at a 1:1 ratio between control and stimulation group. The research teams conducting the rehabilitation protocol at the Hershey Medical Center will instruct and evaluate all participants on how they place the electrodes, operate the NMES device (intensity combo II. This is a commercially available, FDA-approved device), and select the parameters to be used (Table 2 and Figure 2). The intensity will be set to the maximum comfortable intensity by the patient. Additionally, the research team will ensure the participants perform the procedure correctly at each weekly visit. The NMES device has an adherence meter to evaluate adherence to the protocol. Self-applied NMES intervention has been successfully used in several studies targeting muscle weakness after major knee surgeries [53], [54].

Table 2. Proposed NMES protocol

Week	Pad Placement	Time (min) x times per day
1	I, II, III	10 x 1
2-3	I, II, III	10 x 2
4-6	IV	20 x 2

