Self-reported diary and outcomes: To evaluate frequency of loading, from the day after surgery, participants will complete a diary (paper or electronic survey via REDCAP) on estimated daily weightbearing load, number of steps/days with a pedometer placed at the hip, and pain on a visual analogue scale (VAS). Although standard of care prescribes no weight-bearing during the first two weeks after repair, patients are active during that period of time. The level of activity (steps), even though does not involve the use of the injured limb, can help explain potential differences in self-reported outcomes, especially kinesiophobia scores. These measurements are not part of the standard of care. Self-reported outcomes will be also collected at weeks 6 and 12: the Achilles tendon Total Rupture Score (ATRS) [56], the Physical Activity Scale (PAS) [57], the Foot and Ankle Outcome Score (FAOS) Quality of Life subscale [58], and the Tampa Scale of Kinesiophobia (TSK) [59], [60]. Patient reported outcomes (ATRS, PAS and FAOS) are part of the standard of care for Achilles tendon rupture.

Single heel-rise tests: The ability of performing a single heel-rise will be evaluated at week 12. The participants will stand on a flat box with the ankle in neutral position and will be asked to perform a single heel-rise. The participants will be classified as being able to perform a one-legged heel-rise if they were able to lift the heel at least 2 cm once while keeping the knee straight [60]. MuscleLab® (Ergotest Technology, Oslo, Norway) measurement system will be used for the evaluations as previously described in our previous study [29]. This will be performed in the physical therapy clinic at [name]. This test is not part of the standard of care for Achilles tendon rupture.

Table 3. Study Procedures for Stimulation and control groups

Week	Procedure
1	Consenting, Randomization, Distribution of diary and activity monitor, Demonstration of NMES (stimulation group only), (in-person visit)
2, 4	Adjustment of NMES (stimulation group only), collection of steps, and diary data. (Visit 2 can be done virtually with a video call, visit four should be done in person.)
6	Ultrasound Imaging, Questionnaires (ATRS, PAS, FAOS, TSK), collection of steps and diary data, Discontinue use of NMES (stimulation group only). (In-person visit)
12	Ultrasound Imaging, Heel-rise test, Questionnaires (ATRS, PAS, FAOS, TSK) (In person visit)

7.2.1 Visit 1 (Week 1).

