9.2 Data that are reviewed

Describe the data that are reviewed, including safety data, untoward events, and efficacy data.

Achilles tendon healing:

- re-rupture
- deep vein thrombosis
- deep and superficial infection

NMES:

- skin irritation
- excessive pain

Benefits/efficacy:

- self-reported outcomes (questionnaires)
- daily step count
- ability to perform a heel-rise

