10.0 Risks

List the reasonably foreseeable risks, discomforts, hazards, or inconveniences to the subjects related to the subjects' participation in the research. Include as may be useful for the IRB's consideration, a description of the probability, magnitude, duration and reversibility of the risks. Consider all types of risk including physical, psychological, social, legal, and economic risks. Note: Loss of confidentiality is a potential risk when conducting human subject research.

- If applicable, indicate which procedures may have risks to the subjects that are currently unforeseeable.
- If applicable, indicate which procedures may have risks to an embryo or fetus should the subject be or become pregnant.
- If applicable, describe risks to others who are not subjects.

Risk of Randomization: You will be assigned to a treatment program by chance. The treatment you receive may prove to be less effective or to have more side effects than the other research treatment(s) or other available treatments.

Heel-rise test: The heel-rise testing may cause local tendon pain. The subjects will be informed that if they have a pain level above a 5/10 they should inform the evaluator, stop the test, and avoid strong physical activity for 1 or 2 days.

NMES usage: The device used for this test is FDA approved. There is a minimal risk of infection. Discomfort during and muscle soreness after usage lasting a few days after the test may be experienced. Skin irritation caused by the adhesive pads may also occur. Excessive pain might occur during stimulation, even at the recommended settings. Subjects will be instructed to gradually increase the stimulation intensity up to the recommended level by PT. Subjects will be instructed to contact the research team if the excessive pain occurs at or below the recommended intensity.

Tendon healing: Re-injury of the tendon is also a potential risk. The rate of tendon re-rupture in standard therapy is estimated between 2% and 5% [64]. Gapping or non-healing of the tendon have also been observed in regular therapy. These adverse events may be observed in the participants participating in the study. Statistical analysis will be performed to determine if the risk of these adverse events is higher in the intervention group compared to standard therapy.

Additional Risks

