15.5 Process for informing Study Team

Describe the training plans to ensure members of the research team are informed about the protocol and their duties, if applicable.

Training of therapists and participants on applying the NMES protocol

NMES applied at home by the participants themselves are common clinical practice. Research team are trained to provide and monitor such interventions. Typically, research teams demonstrate the procedure to the participants, participants will perform the procedure by themselves, and the research team verifies that the procedure is applied properly and corrects any problems with the protocol. The research team will verify and adjust the protocol during subsequent visits scheduled as part of regular physical therapy visit.

Ultrasound Imaging.

[name] and [name] will agree on the protocols for ultrasound data collection according to the established protocols that have been used in previous studies [65]–[70].

Other data collection instruments

Members of the team will be trained on using REDCap which will be used to record other data collection instruments such as questionnaires and to store data from imaging session and functional tests.

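### Excessive pain is defined and prompted for only as an NMES event, so the between-arm adverse event odds ratio can be inflated against NMES by unequal ascertainment

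*Combined protocol and SAP*

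**What the plan says.** **Where excessive pain appears.** Section 9.1 names two groups of monitored events: those of tendon healing, and those linked to the device, "or the use of NMES (skin irritation and excessive pain". Section 9.2 repeats the split and puts "excessive pain" under NMES. Section 9.1 gives standard-of-care rates for re-rupture (5%), DVT (48%), infection (2.8%) and skin irritation (33%), but none for excessive pain. The only number attached to the term is the removal criterion in 3.3.1, "excessive pain during stimulation (>5/10".

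**Who is prompted.** Section 10, under NMES usage, says: "Subjects will be instructed to contact the research team if the excessive pain occurs at or below the recommended intensity". Both arms are told to report pain above 5/10, but only at the week-12 heel-rise test.

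**How harm is compared.** Section 8.3: "The planned interim safety analyses will quantify the odds ratio between adverse events in the intervention group and standard of care". A lower 95% limit above 1.0 is read as significantly more AEs with NMES. Section 9.7 applies the same test. Section 9.8 suspends the study if the odds ratio for intervention-related AEs and/or SAEs is significant. Section 7.4.5 gives blinding as not applicable.

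**What is common to both arms.** Section 7.2 has participants keep a daily diary that includes weight-bearing, steps "and pain on a visual analogue scale (VAS", and 9.4 puts this in the first six weeks. Table 3 gives both arms the same visits, and 9.1 has all AEs captured at every visit.

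**The concern.** A between-arm odds ratio measures harm only if an event has the same chance of being counted in either arm. Here a participant in the NMES arm with pain above 5/10 during a session has an event category, a threshold and a prompt to call. A control with the same pain has none of these, and no passage says when control pain becomes an AE. The team also knows the arm when it decides what to record.

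Two consequences follow. The plan could state that AEs are significantly more frequent with NMES when they are not. It also cannot say how much of the pain in the NMES arm is due to NMES, because no matching control rate is defined. In 9.8 the imbalance is partly structural as well: controls can hardly have an AE related to the intervention.

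**Working it through.** The plan states no operating characteristics for its harm rule, so there is no figure of its own to reproduce.

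**Inputs from the plan**
- 25 per arm (8.3).
- Rule: lower 95% limit of the odds ratio above 1 (8.3, 9.7).
- Re-rupture 5%, infection 2.8%, DVT 48% (9.1), taken as equal in both arms.

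**Assumptions, because the documents are silent**
- True rate r of excessive pain, equal in both arms: 10%, 20% or 30%.
- All of it counted with NMES; a share s counted in controls.
- Events independent, and one look at the data.
- Skin irritation left out.

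**Formulas**
- Chance of at least one other event: q = 1 − 0.95 × 0.972 = 0.0766. With DVT: q = 1 − 0.52 × 0.95 × 0.972 = 0.520.
- Counted rate with NMES: pN = 1 − (1 − q)(1 − r).
- Counted rate in controls: pC = 1 − (1 − q)(1 − s·r).
- Odds ratio: pN(1 − pC) / [pC(1 − pN)].
- Chance that the rule fires: sum of the two binomial probabilities (n = 25 each) over all outcomes whose Wald 95% interval for the log odds ratio lies above 0, with 0.5 added to each cell when any cell is zero.

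**Worked case, r = 20%, no DVT.** pN = 1 − 0.9234 × 0.8 = 0.2613.
- s = 0: pC = 0.0766, so the odds ratio is (0.2613 × 0.9234)/(0.0766 × 0.7387) = 4.26.
- s = 0.5: pC = 1 − 0.9234 × 0.9 = 0.1689, so the odds ratio is (0.2613 × 0.8311)/(0.1689 × 0.7387) = 1.74.

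**Odds ratio, and chance that the rule fires, with equal true harm**

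| Other events | Control pain recorded | r = 10% | r = 20% | r = 30% |
|---|---|---|---|---|
| No DVT | none | 2.45; 6.3% | 4.26; 31.6% | 6.59; 64.2% |
| No DVT | half | 1.45; 3.2% | 1.74; 9.7% | 2.00; 17.7% |
| No DVT | three quarters | 1.19; 2.1% | 1.29; 4.7% | 1.38; 7.3% |
| No DVT | all | 1; 1.4% | 1; 2.1% | 1; 2.5% |
| With DVT | none | 1.21; 4.9% | 1.48; 9.8% | 1.82; 17.7% |
| With DVT | half | 1.10; 3.5% | 1.22; 5.3% | 1.36; 7.7% |
| With DVT | three quarters | 1.05; 2.9% | 1.11; 3.8% | 1.17; 4.6% |
| With DVT | all | 1; 2.4% | 1; 2.6% | 1; 2.5% |

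**Sensitivity, pain analysed alone, 90% recorded with NMES.** At r = 10% the rule fires in at most 0.5% of trials, even if no control pain is recorded. At r = 30% with half of control pain recorded it fires in 14.5% at one look. It fires in 18.1% over six looks, simulated at an assumed 4, 8, 12, 16, 20 and 25 per arm to mimic the two-monthly review.

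**Are there extra NMES contacts?** Section 7.2 says "the research team will ensure the participants perform the procedure correctly at each weekly visit", and 7.1 has stimulation settings updated weekly. Table 3 schedules NMES adjustment only at weeks 2 and 4, within visits that both arms attend. Section 15.5 adds: "The research team will verify and adjust the protocol during subsequent visits scheduled as part of regular physical therapy visit". Standard rehabilitation is given to both arms, however, and 18.2 has subjects evaluated at those visits without limit by arm.

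**The case against.** The best defence is that AE capture is general. Section 9.1 captures all AEs at every visit, 18.2 has the team evaluate subjects at standard rehabilitation visits, and neither is limited by arm. The lists in 9.1 and 9.2 do not exclude control pain, and the 5/10 figure is a removal criterion, not an AE definition. Some control pain will therefore be recorded. This stands, and it makes the rows with no control pain an upper bound. It does not remove the problem, because a defined and prompted event is still compared with an undefined one.

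The diary is not ignored either: VAS pain is a secondary endpoint, and 9.4 places the daily record within the safety plan. What is missing is a rule that turns it into a harm count. The heel-rise instruction covers both arms, but it applies at week 12, after stimulation has stopped at week 6.

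Pain caused by stimulation is also a real device harm, and its absence in controls is not in itself bias. That is a reason to report it separately, not to mix it with pain that both arms can have.

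A reader might infer that controls are seen less often than NMES participants. The documents do not establish this. The weekly wording in 7.1 and 7.2 conflicts with Table 3, and the passages must be reconciled. A reader might also take 64% as the chance that the trial is wrongly suspended. It is not: 9.8 counts intervention-related AEs and/or SAEs, and a physician judges relatedness first, whereas the calculation pools all events.

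**Conclusion.** The concern holds in this form: the AE odds ratio **can** be inflated against NMES because excessive pain is defined and prompted for in one arm only. The documents do not support saying that it **will** be, since they do not say whether control pain above a threshold counts as an AE.

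If half of control pain is recorded, the chance of a false statement of excess AEs under 8.3 and 9.7 is 3% to 18% without DVT and 4% to 8% with it, against about 1.4% to 2.6% under symmetric counting. The upper bounds are 6% to 64% and 5% to 18%. All of these rest on assumed pain rates of 10% to 30%, assumed recording shares, independent events and one look. Pooling DVT dilutes the effect, and no passage says which AEs enter the ratio. Whatever the size, an excess of pain due to NMES cannot be separated from pain after surgery as the plan stands.

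**What to change.** Amend 8.3, 9.1, 9.2 and 9.7, and the reporting instruction in section 10:

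1. For the between-arm comparison, define excessive pain in both arms from the existing daily VAS diary, with one threshold (for example above 5/10) and one window. Start the window after the week-1 visit at which NMES is demonstrated and end it at week 6. The diary begins the day after surgery, so a window over all of weeks 1 to 6 would count pain from before NMES and could mask an effect.
2. Elicit AEs with the same questions at the common visits (weeks 2, 4, 6 and 12), and give both arms the same instruction to report pain or other events between visits.
3. Base the between-arm odds ratio on events that both arms can have and that are ascertained alike. Report stimulation pain and pad-related events separately as NMES-arm tolerability, with action on individual participants unchanged.
4. Record the contact at which each AE was first reported, and use it in a sensitivity analysis. Do not exclude AEs on a judgement of whether a common visit would have found them; nobody can adjudicate that.
5. Reconcile the weekly wording in 7.1 and 7.2 with Table 3.

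The cost is wording and one field on the AE form, with no new visit or measurement. The downside is small: the diary covers weeks 1 to 6 only, and device-specific events move from the odds ratio to a separate listing.
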